2.8.4 Other safety data

2.8.4.1 Vital signs

Vital sign assessments are performed in order to characterize basic body function. The following parameters were collected: body temperature (°C), systolic and diastolic blood pressure (mmHg).

For analysis of vital signs, notable criteria are provided in Table 1-2 below.

Table 2-1 Clinically notable changes in vital signs

Vital sign (unit)	Clinically notable criteria	
	above normal value	below normal value
Systolic blood pressure (mmHg)	>=180 with increase from baseline of >=20	<=90 with decrease from baseline of >=20
Diastolic blood pressure (mmHg)	>=105 with increase from baseline of >=15	<=50 with decrease from baseline of >=15
Body temperature	>= 39.1	-

The number and percentage of subjects with notable vital sign values (high/low) will be presented for the Safety Set.

A listing of all vital sign assessments will be produced and notable values will be flagged. In the listing, the assessments collected during the post-treatment period will be flagged.

2.8.4.2 ECOG performance status

The ECOG PS scale will be used to assess the physical health of patients, ranging from 0 (most active) to 5 (least active):

Table 2-2 ECOG Performance Scale

Score	Description
0	Fully active, able to carry on all pre-disease performance without restriction
1	Restricted in physically strenuous activity but ambulatory and able to carry out work of a light or sedentary nature, e.g., light house work, office work
2	Ambulatory and capable of all self-care but unable to carry out any work activities. Up and about more than 50% of waking hours
3	Capable of only limited self-care, confined to bed or chair more than 50% of waking hours
4	Completely disabled. Cannot carry on any self-care. Totally confined to bed or chair
5	Dead

ECOG scores over time will only be listed.

2.9 Pharmacokinetic endpoints

Not Applicable

2.10 PD and PK/PD analyses

Not Applicable

2.11 Patient-reported outcomes

[figure not shown]
The Myelofibrosis 7 Item Symptom Scale (MF-7) along with Modified MFSAF v2.0 (computed through the addition of a separate question on Inactivity to the data captured with MF7) and the PGIC will be primarily used to collect electronically the patient's disease-related symptoms and patient impression of change. No formal statistical test will be performed.

Missing items data in a scale will be handled based on each instrument manual. No imputation will be applied if the total or subscale scores are missing at a visit. The FAS will be used for analyzing PRO data. Descriptive statistics (e.g., mean, median) will be used to summarize the scored scales at each scheduled assessment time point for the Myelofibrosis 7 Item Symptom Scale (MF-7) and the Modified MFSAF v2.0 score.

Change from baseline in the domain scores at the time of each assessment will be summarized. Patients with an evaluable baseline score and at least one evaluable post-baseline score during the treatment period will be included in the change from baseline analyses. The number and

percentage of patients in each PGIC response category at selected time points will be summarized.

Proportion of patients with at least 50% reduction in MF-7 and modified MFSAF v2.0 from baseline will also be reported at Week 24 along with its 95% CI using exact Clopper-pearson method.

2.13 Other Exploratory analyses

Not Applicable.

2.14 Interim analysis

No formal interim analysis is planned for this trial.

The primary analysis will be performed after all patients have completed Week 24 or discontinued prior to Week 24. Any other interim updates may be provided to fulfill regulatory obligations to comply with post-approval commitments, or for publication purposes.

The final analysis will occur at the end of the study. All available data from all patients will be analyzed and summarized in a final CSR.

3 Sample size calculation

Approximately 50 patients will be enrolled in this study. Success at Week 24 will be declared if the following criteria are met:

- a. Observed proportion of patients with $\geq 50\%$ reduction in spleen length at Week 24 $\geq 25\%$
- b. Probability of true response rate $\leq 15\%$ (considered not clinically meaningful) is less than 10%

With 50 patients, criteria 'a' and 'b' will be met if the observed responder rate is $\geq 25\%$, i.e. if at least 13 patients out of 50 patients have a response at Week 24.

Sample Size	No. of responders	Observed responder rate (%)	Probability of true responder rate $\leq 15\%$
N=50	11	22	0.1014
	12	24	0.0520
	13	26	0.0243

	14	28	0.0104
	15	30	0.0041
	16	32	0.0015

The operating characteristics of the design are presented in the table below. This table shows the probability for positive conclusion (i.e. success criteria met at the end of the study) under different true responder rates. When the true responder rate at Week 24 is $\leq 15\%$, the probability of positive conclusion is $\leq 10\%$ (false success rate). The probability of success is $> 90\%$ when the true responder rate at Week 24 is 35%.

Sample Size	True responder rate (%)	Probability of positive conclusion
N=50	15	0.0301
	20	0.1861
	25	0.4890
	30	0.7771
	35	0.9339
	40	0.9867
	45	0.9982
	50	0.9998

4 Change to protocol specified analyses

Not Applicable.

5 Appendix

5.1 Imputation rules

5.1.1 Study drug

The following rule should be used for the imputation of the dose end date for a given study treatment component:

Scenario 1: If the dose end date is completely missing and there is no EOT page and no death date, the patient is considered as on-going:

The patient should be treated as on-going and the cut-off date should be used as the dose end date.

Scenario 1 should not applicable for final CSR. All patients should have EOT page complete before the Database lock for Final CSR

Scenario 2: If the dose end date is completely or partially missing and the EOT page is available:

Please note that date of assessment on EOT CRT might be very different from last date of dose.

Case 1: The dose end date is completely missing, and the EOT completion date is complete, then this latter date should be used.

Case 2: Only Year(yyyy) of the dose end date is available and yyyy < the year of EOT date:

Use Dec31yyyy

Case 3: Only Year(yyyy) of the dose end date is available and yyyy = the year of EOT date:

Use EOT date

Case 4: Both Year(yyyy) and Month (mm) are available for dose end date, and yyyy = the year of EOT date and mm < the month of EOT date:

Use last day of the Month (mm)

All other cases should be considered as a data issue and the statistician should contact the data manager of the study.

After imputation, compare the imputed date with start date of treatment, if the imputed date is < start date of treatment:

Use the treatment start date

Patients with missing start dates are to be considered missing for all study treatment component related calculations and no imputation will be made. If start date is missing then end-date should not be imputed.

5.1.2 AE, ConMeds and safety assessment date imputation.

Table 5-1 Imputation of start dates (AE, CM) and assessments (LB, EG, VS)

Missing Element	Rule
day, month, and year	
• No imputation will be done for completely missing dates
day, month	
• If available year = year of study treatment start date then
◦ If stop date contains a full date and stop date is earlier than study treatment start date then set start date = 01JanYYYY◦ Else set start date = study treatment start date.• If available year > year of study treatment start date then 01JanYYYY• If available year < year of study treatment start date then 01JulYYYY
day	
• If available month and year = month and year of study treatment start date then
◦ If stop date contains a full date and stop date is earlier than study treatment start date then set start date= 01MONYYYY.◦ Else set start date = study treatment start date.• If available month and year > month and year of study treatment start date then 01MONYYYY

Missing Element	Rule
	
• If available month and year < month year of study treatment start date then 15MONYYYY

Table 5-2 Imputation of end dates (AE, CM)

Missing Element	Rule (*=last treatment date plus 30 days not > (death date, cut-off date, withdrawal of consent date))
day, month, and year	Completely missing end dates (incl. ongoing events) will be imputed by the end date of the on-treatment period*
day, month	If partial end date contains year only, set end date = earliest of 31DecYYYY or end date of the on-treatment period *
day	If partial end date contains month and year, set end date = earliest of last day of the month or end date of the on-treatment period*

Any AEs and ConMeds with partial/missing dates will be displayed as such in the data listings.

Any AEs and ConMeds which are continuing as per data cut-off will be shown as 'ongoing' rather than the end date provided.

5.1.2.1 Other imputations

Not applicable

5.2 AEs coding/grading

Adverse events are coded using the Medical dictionary for regulatory activities (MedDRA) terminology.

AEs will be assessed according to the Common Terminology Criteria for Adverse Events (CTCAE) version 4.03.

The CTCAE represents a comprehensive grading system for reporting the acute and late effects of cancer treatments. CTCAE grading is by definition a 5-point scale generally corresponding to mild, moderate, severe, life threatening, and death. This grading system inherently places a value on the importance of an event, although there is not necessarily proportionality among grades (a grade 2 is not necessarily twice as bad as a grade 1).

5.3 Laboratory parameters derivations

Grade categorization of lab values will be assigned programmatically as per NCI Common Terminology Criteria for Adverse Events (CTCAE) version 4.03. The calculation of laboratory CTC grades will be based on the observed laboratory values only, clinical assessments will not be taken into account. The criteria to assign CTC grades are given in <Novartis internal criteria

for CTC grading of laboratory parameters>. The latest available version of the document based on the underlying CTCAE version 4.03 at the time of analysis will be used.

For laboratory tests where grades are not defined by CTCAE v4.03, results will be graded by the low/normal/high (or other project-specific ranges, if more suitable) classifications based on laboratory normal ranges.

A severity grade of 0 will be assigned for all non-missing lab values not graded as 1 or higher. Grade 5 is not applicable. For laboratory tests that are graded for both low and high values, summaries will be done separately and labeled by direction, e.g., sodium will be summarized as hyponatremia and hypernatremia.

Imputation Rules

CTC grading for blood differential is based on an absolute value. However, these data may not be reported as absolute counts but rather as percentage of WBC.

If laboratory values are provided as '<X' (i.e. below limit of detection) or '>X', prior to conversion of laboratory values to SI unit, these numeric values are set to X.

The following rules will be applied to derive the WBC differential counts when only percentages are available for a xxx differential.

$$\text{xxx count} = (\text{WBC count}) * (\text{xxx \%value} / 100)$$

Further derivation of laboratory parameters might be required for CTCAE grading. For instance, corrected calcium can be derived using the reported total calcium value and albumin at the same assessment using the following formula:

$$\text{Corrected Calcium (mg/dL)} = \text{Calcium (mg/dL)} - 0.8 [\text{Albumin (g/dL)} - 4]$$

In order to apply the above formula, albumin values in g/L will be converted to g/dL by multiplying by 0.1, calcium values in mmol/L will be converted to mg/dL by dividing by 0.2495. For calculation of laboratory CTC grades 0 and 1, the normal range for derived corrected calcium is set to the same limits (in mg/dL) as for calcium.

CTC grades for derived absolute WBC differential counts (neutrophils, lymphocytes) and corrected calcium will be assigned as described above for grading.

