7.2.2.7 Laboratory evaluations

Clinical laboratory tests (hematology, clinical chemistry, viral hepatitis and pregnancy testing) will be performed at the center where the patient is enrolled (local laboratory).

All patients will have samples of blood collected on the days noted in the Visit Evaluation Schedule [Table 7-1](#). [Table 7-2](#) provides a complete list of laboratory tests that will be performed at the local laboratory.

Hepatitis B testing – At screening, HBV infection status testing will be done for HB-sAG and anti HB-c antibody. If HB-sAG is negative and anti HB-c antibody is negative, the patient can be enrolled.

If HB-sAG is positive and/or anti HB-c antibody is positive, the site will determine per local procedures if infection is active (with viral replication) or inactive (without viral replication). Possible test include, for instance, serology testing for HB-eAG and PCR for HBV DNA.

Patients with active HBV infection (with viral replication) are not eligible for enrollment.

Patients with inactive HBV infection (without viral replication) can be enrolled. Monitoring of these patients for reactivation by regular testing, using the same test is required **every 12 weeks**. Treatment in case of reactivation will be as per local procedure. This information will be collected in the eCRF.

[figure not shown]
Hepatitis C testing – At screening, HCV infection status will be assessed by the means of anti HCV antibody screen. The patient can be enrolled if anti HCV antibody is negative. If anti HCV antibody is positive then HCV RNA by PCR will be performed.

Patients with active HCV infection (with viral replication) are not eligible for enrollment.

Patients with inactive HCV infection (without viral replication) can be enrolled. Monitoring of these patients for reactivation is required by means of HCV RNA by PCR at regular intervals as per the local practice. This information will be collected in the eCRF.

Table 7-2 Local Clinical laboratory parameters collection plan

Test Category	Test Name
Hematology	Hematocrit, Hemoglobin, MCH, MCHC, MCV, Platelets, Red blood cells, White blood cells, RBC Morphology, Blasts, Differential (Basophils, Eosinophils, Lymphocytes, Monocytes, Neutrophils, Bands, Other (absolute value preferred , %s are acceptable).

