5.5 Dynamic International Prognostic Scoring System (DIPSS)

- The Dynamic International Prognostic Scoring System (DIPSS) can be used to assess a patient's prognosis as conditions change over time.
- DIPSS risk score will be derived for both Primary and secondary MF patients at baseline

Risk Factor		Points	
	0	1	2
Hemoglobin	≥ 10 g/dL	...	< 10 g/dL
WBC count	$\leq 25 \times 10^9$ L	$> 25 \times 10^9$ L	...
Constitutional symptoms	No	Yes	...
Age	≤ 65 years	> 65 years	...
Peripheral blood blasts	< 1 %	≥ 1 %	...

The risk level is assigned by the total score:

Risk Group	Points	Median Survival, Years
High	5-6	1.5
Intermediate 2	3-4	4
Intermediate 1	1-2	14.2
Low	0	NR

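### SAP 5.3 sets a laboratory result reported as '<X' equal to X, so a blast count of '<1%', if passed to the DIPSS table, scores a point it should not

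*SAP*

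**What the plan says.** SAP 5.3, under its imputation rules, covers results reported as limits: "If laboratory values are provided as '<X' (i.e. below limit of detection) or '>X"' is the trigger, and the action is that "prior to conversion of laboratory values to SI unit, these numeric values are set to X". No parameter is exempted, and the rule does not distinguish results that are averaged from results that are compared with a cut. The same section assigns grades by program: "The calculation of laboratory CTC grades will be based on the observed laboratory values only, clinical assessments will not be taken into account". It does not print the grade cuts: "The criteria to assign CTC grades are given in <Novartis internal criteria" for laboratory parameters, a document based on CTCAE v4.03 that is not supplied.

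SAP 5.5 states that "DIPSS risk score will be derived for both Primary and secondary MF patients at baseline". Its table has the row "Peripheral blood blasts < 1 % ≥ 1" %, where the first column is worth 0 points and the second 1 point. It says nothing about blast results reported as a limit and does not refer to 5.3.

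Blasts are a laboratory value within the scope of 5.3: Table 7-2 in Protocol 7.2.2.7 lists "RBC Morphology, Blasts, Differential" in the local hematology panel.

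**The concern.** A result of '<1%' states that the blast percentage is below 1, so it belongs in the 0-point column. Replacing it by 1 moves it across the cut. The error always goes the same way: it can add a DIPSS point but never remove one for blasts. The cohort's baseline prognostic description would then be shifted upward by a data-handling convention.

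The same logic applies wherever a reported limit coincides with a strict cut. A low count reported as '<X' would be graded as if it were exactly X, which falls outside a category defined as below X.

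**Working it through.** No figure printed in the plan is in dispute. The check is to apply the rule literally and see where the result lands.

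**Inputs**
- Substitution: '<X' becomes X; '>X' becomes X (SAP 5.3).
- DIPSS points (SAP 5.5): hemoglobin <10 g/dL, 2; WBC >25 × 10⁹/L, 1; constitutional symptoms, 1; age >65 years, 1; blasts ≥1%, 1.
- Risk groups (SAP 5.5): Low 0; Intermediate 1, 1–2; Intermediate 2, 3–4; High 5–6.
- Entry requires hemoglobin <10 g/dL (Protocol 5.2, criterion 4).

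**Step 1, the blast point.** Reported '<1%': the true value is below 1, so 0 points. After substitution the value is 1.0; 1.0 ≥ 1 holds, so 1 point.

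**Step 2, the risk group.** Let s be the number of the other three factors present (WBC, symptoms, age). The correct total is 2 + s; the total after substitution is 2 + s + 1.

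| s | Patterns | Correct total and group | After substitution | Group changes? |
|---|---|---|---|---|
| 0 | 1 | 2, Intermediate 1 | 3, Intermediate 2 | Yes |
| 1 | 3 | 3, Intermediate 2 | 4, Intermediate 2 | No |
| 2 | 3 | 4, Intermediate 2 | 5, High | Yes |
| 3 | 1 | 5, High | 6, High | No |

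The group changes in 1 + 3 = 4 of 8 patterns. This counts patterns, not patients; the share of affected patients who change group depends on how common the three factors are.

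Example: age 60, hemoglobin 9.0 g/dL, WBC 8 × 10⁹/L, no constitutional symptoms, blasts '<1%'. Correct score 2 (Intermediate 1); score under the rule 2 + 1 = 3 (Intermediate 2).

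SAP 2.1.1 takes the last assessment on or before first dose as baseline. If a patient's hemoglobin had reached 10 g/dL by then, the totals would be s and s + 1. The group would change at 0 to 1 and at 2 to 3, again 1 + 3 = 4 of 8 patterns.

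**Step 3, grades.** The v4.03 cuts are not available. The only cuts printed are in the product information (Protocol Appendix 6), under CTCAE v3.0, and serve as illustration only. Neutrophils '<500' become 500, which is not below 500, so grade 3 instead of 4. Platelets '<25,000' become 25,000, so grade 3 instead of 4. When X lies below the cut, the substituted value is also below it and the grade is right. The problem therefore needs X to equal the cut. The mirror case for '>X' is the liver summary in SAP 2.8.3: a result reported as above a limit equal to 3 × ULN would not count as >3 × ULN.

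**Step 4, how many patients.** Neither document says how often sites report blasts as '<1%'. Of the 50 planned patients, the number affected could be anything from 0 to 50.

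**The case against.** The strongest reply concerns scope. The rule carries the gloss that '<X' means below a detection limit, it sits among text on CTC grading, differential counts and corrected calcium, and 5.5 does not say that it uses substituted values. A programmer could match a reported '<1%' directly to the column headed below 1% and score 0. Nothing shows that 1% is a reporting limit at any site. All of this stands, and it is why the point is conditional on the substituted value reaching the DIPSS table. It does not remove the point: the wording covers laboratory values without exception, and 5.5 contains nothing that overrides it.

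The second reply is that little depends on DIPSS. It is derived at baseline, SAP 2.2.4 plans no subgroups, and no listed endpoint uses it. This also stands. A reader might infer that the rule makes the cohort look misleadingly like the phase III populations. The visible text plans no comparison by risk group, and the documents describe those trials by IPSS or IWG categories, so that inference goes too far.

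A reader might also infer that the rule hides grade 4 cytopenias. The documents do not support that. Neutrophil counts below 500/µL and platelets below 25,000/µL call for interruption (Protocol 6.3.1.1). An abnormality for which the protocol requires a dose hold must be reported as an adverse event (Protocol 8.1.2.1). That event has its own severity grade and is summarized by maximum grade (SAP 2.8.1). A value moved from grade 4 to grade 3 would still appear in the grade 3 or 4 laboratory listing (SAP 2.8.3).

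**Conclusion.** The concern holds as a boundary error in a stated rule. Read as written and applied to DIPSS, it turns a blast result known to be below 1% into one that scores a point, and it raises the risk group in 4 of the 8 patterns of the remaining factors. This rests on two conditions that the documents do not settle: that at least one laboratory reports blasts as '<1%', and that the DIPSS program uses the substituted value. If laboratories report 0 or exact values, the effect is nil. It is tempting to estimate a patient count by assuming a reporting frequency, but any such count would be a product of assumptions with no basis in the documents.

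The effect on DIPSS is confined to the baseline description; the spleen-length primary endpoint is untouched. The grading version is a rare boundary case and cannot be checked without the v4.03 criteria. Overall this is a minor clarification, worth making because it costs almost nothing.

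**What to change.** In SAP 5.3, add that for every threshold classification (DIPSS points, CTC grades, normal-range flags) a result reported as '<X' is treated as strictly below X and one reported as '>X' as strictly above X. The substituted value X is then used only for numerical summaries and plots. In SAP 5.5, add that blasts reported as '<1%' score 0. The cost is two sentences and a small programming change; no additional data are needed.

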5.4 Time windows for box plots

All scheduled/unscheduled assessments should be assigned to time windows. In case of multiple values per window, the one closest to the planned visit date should be used. If 2 values are equidistant to the planned visit date, the selection should be made by selecting the one assessed by central (if any) and otherwise - for multiple central assessments or ECGs / vital signs equidistant to the planned visit - the last value.

Boxplots should display boxes (25th – 75th percentiles) and median (line) as well as joint mean (dot) values. Whiskers extend to the 5th – 95th percentiles with any values outside the whiskers not being displayed. A footnote to the box plot should explain that these values are not displayed. However, all values are used to calculate mean and percentiles displayed on the graph, and

corresponding summary tables should be generated. The number of observations used for this analysis is to be stated at the bottom.

5.5 Dynamic International Prognostic Scoring System (DIPSS)

- The Dynamic International Prognostic Scoring System (DIPSS) can be used to assess a patient's prognosis as conditions change over time.
- DIPSS risk score will be derived for both Primary and secondary MF patients at baseline

Risk Factor		Points	
	0	1	2
Hemoglobin	≥ 10 g/dL	...	< 10 g/dL
WBC count	$\leq 25 \times 10^9$ L	$> 25 \times 10^9$ L	...
Constitutional symptoms	No	Yes	...
Age	≤ 65 years	> 65 years	...
Peripheral blood blasts	< 1 %	≥ 1 %	...

The risk level is assigned by the total score:

Risk Group	Points	Median Survival, Years
High	5-6	1.5
Intermediate 2	3-4	4
Intermediate 1	1-2	14.2
Low	0	NR

